Hypothesis 1a: The ID-Cap-M system will detect over 95% of medication ingestion events as ascertained by doses of medication recorded by the ID-Cap System that are taken as prescribed (once daily and on time with use of ID-Cap System as instructed) over those scheduled.

Hypothesis 1b: The ID-Cap-M system will have an advantage over the MEMS caps on monitoring and enhancing medication adherence expressed by a proportion of daily medication doses reported by the system to be ingested (ID-Cap System) or accessed (MEMS Caps) as prescribed (defined as within the scheduled administration time) over the study period.

Exploratory Aim 2: To assess the safety of the ID-Cap-M system when used in a healthy population by documenting the frequency and severity of adverse events.

Exploratory Hypothesis 2: Participants randomized to receive the ID-Cap-M system will report similar rates of adverse events as participants randomized to receive standard capsules.

Overview: The primary objective of the clinical trial is to evaluate the acceptability, tolerability, and efficacy of the ID-Cap-M in a healthy population. The primary outcome will be medication compliance as measured by the proportion of days adherent to taking medication over a four week period.

Subjects: 40 participants between the ages of 18 and 65 will be recruited over a 10-month period. Additional inclusion criteria include ability to provide informed consent, functioning at an intellectual

Program Director/Principal Investigator (Last, First, Middle): [name]

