software needed to transfer data. Providing the necessary technology will prevent the exclusion of individuals without smartphone access or those who cannot afford to pay for a smartphone data plan. Group 2 will also provide biometric data for compliance measurement, specifically ECG. These measurements will be collected by their eTect reader.

Study visits: The study duration will be approximately six weeks. At the initial randomization visit, participants will be trained on use of the devices (MEMS 6 TrackCap for Group 1 and biometric data collection/ID-Cap-M for Group 2) and medication administration will be observed. A 30-day supply of study capsules will be dispensed. Participants will be instructed to take each dose by 12PM daily. Participants will return to the clinic approximately five weeks (within one week following last dose) after their initial randomization for an End of Study (EOS) visit to discuss overall medication compliance and return their study equipment (pill bottles, unused capsules if any, and MEMS 6 TrackCap or ID Cap Reader). For those in Group 2, passage of ID-Caps will be confirmed at this visit via abdominal x-ray.

Safety Assessment: Adverse events (AEs) will be assessed at the End of Study visit. The research clinician will identify potential adverse events by asking the subject a question such as: "Have you had any problems or side effects since we saw you last (such as flu, headache, nausea, or other problems)?" The type of AE, severity of AE, and relationship to the study intervention will be recorded. At their initial randomization visit, subjects will be given detailed information regarding clinic contact procedures during and afterhours should this be necessary during their study participation. An abdominal X-ray will also be completed at study completion to verify passage of the capsules from the gastrointestinal tract for those in Group 2.

Follow-up Plan: In the event that an adverse event occurs during the study, a subject will be followed to resolution. Participants will be provided incentive compensation to attend the EOS visit and return the MEMS 6 TrackCap or e-Tect reader and cell phone (if one was provided).

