Compensation: Subjects will be compensated \$30 for screening, (\$20 for interview, \$10 for H&P). They will be compensated \$250 for the End of Study visit (\$100 for attendance and \$150 for return of their MEMS 6 TrackCap or ID Cap Reader). If a Group 2 subject did not return for an unscheduled urine sample as requested during the study, they will receive \$50 for attending the EOS visit (versus \$100).

Data Management and Reduction: All paper-based assessments (other than laboratory reports) will be entered into REDCap, a secure, web-based application designed exclusively to support data capture for research studies. REDCap provides an intuitive interface for data entry (with data validation), audit trails for tracking data manipulation, and automated export procedures for data downloading to statistical packages such as SPSS and SAS. Completed assessments will be entered within two weeks after the information has been collected from the subject. Quarterly database management and data integrity audits will be conducted and reports submitted.

Statistical Methods: Univariate descriptive statistics and frequency distributions will be calculated for all variables. Departures from distributional assumptions for the proposed parametric methods will be identified and appropriate transformations of the data will be applied or alternative procedures (semi/non parametric methods) will be employed. Values for demographic, clinical, and other prognostic variables will be compared for imbalance across treatment groups. ***Aim 1:*** The hypothesis

Program Director/Principal Investigator (Last, First, Middle): [name]

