that the ID-Cap-M will improve compliance will be tested by comparing the number of medication adherent days (defined as ingestion of dose of medication within one hour of scheduled time) in the group receiving the ID-Cap-M with the group using a MEMS 6 TrackCap. The primary analysis of the difference in the number of adherent days will be done using a two group ANOVA model. Additional model analysis will be conducted assuming a binary pattern of responses on each day and fit into a Generalized Linear Model using a Generalized Estimating Equations (GEE) framework. **Exploratory Aim 2:** To test the safety and tolerability of ingestion of the ID-Cap-M versus standard capsules, the number of adverse event reported in the 20 subjects taking the ID-Cap will be compared to the number of events in the 20 subjects assigned to standard capsules. Analysis will be performed using a Pearson Chi-Square test statistic.

Other Statistical Considerations: The primary method of analysis will be through the use of the intent to treat sample where missing compliance data will be deemed non-adherent. However, other methods of missing data analysis will be employed and a sensitivity analysis of the various methods will be presented.

Sample Size Justification: The proposed study intends to evaluate the feasibility of inclusion of ID-Caps to monitor compliance in medication trials involving substance abusing subjects. The current study is a 30-day efficacy evaluation of the ID-Cap-M versus MEMS 6 TrackCap. **Aim 1:** With 20 subjects receiving the active ID-Caps and 20 receiving MEMS 6 TrackCap, we will have 80% power with a two sided $\alpha=0.05$ to detect an effect size of 0.95 (Cohen's *d*), which is equivalent to a difference of 0.95 adherent days between the two study groups for each unit in the standard deviation (example: with a SD of 10 days, we will be able to detect a difference of 9.5 days between groups)..

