Design Considerations: *Choice of study population.* The determination was made to conduct this initial tolerability and feasibility trial in healthy individuals. After establishment of safety and efficacy in this population, subsequent studies will be conducted in drug-dependent populations. *Use of riboflavin.* Riboflavin is a water-soluble vitamin; it has no psychoactive properties and is excreted in the urine. A dose of up to 150 mg riboflavin daily has been shown to be well-tolerated by patients and easily measurable in patients' urine at levels 10-fold greater than normal using chromatographic separation and flurometric detection (Anton, 1996). As riboflavin is commonly used as a compliance measure in medication studies (Dubbart et al, 1985; Del Boca et al, 2006), it was considered an appropriate comparison marker to include.

Timeline: As we have an active recruitment network and trained staff in place, we anticipate minimal time required for study start-up. Given our previous recruitment rates for non-treatment studies (7 participants/month) we anticipate completion of the clinical trial within 12 months.

HUMAN SUBJECTS RESEARCH

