- 2) The research material will be obtained specifically for research purposes. Written research material obtained will be stored in the Addiction Sciences Division, in an office that is locked when not in use. Any quantitative riboflavin urine samples collected during the study will be stored in the MUSC Clinical Neurobiology Laboratory..

c. Potential Risks

Potential risks associated with capsule ingestion include discomfort in the form of pressure sensations in the esophagus upon ingestion (typically lasting less than 30 seconds), risk of endoscopy pill retention, and a rare risk of capsule aspiration upon attempting to swallow the capsule. There is the risk of breach of confidentiality.

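### Exploratory Hypothesis 2 predicts similar adverse-event rates, but the planned chi-square with 20 per arm tests for a difference and cannot show similarity; the unit of analysis also needs fixing.

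*Combined protocol and SAP*

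**What the plan says.** All references are to the combined protocol and SAP.

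- **Aim and hypothesis (opening section).** Exploratory Aim 2 assesses safety "by documenting the frequency and severity of adverse events". Exploratory Hypothesis 2 says that participants given the ID-Cap-M "will report similar rates of adverse events" as those given standard capsules.
- **Statistical Methods, Exploratory Aim 2.** Here "the number of adverse event reported in the 20 subjects taking the ID-Cap will be compared to the number of events" in the other 20. "Analysis will be performed using a Pearson Chi-Square test statistic".
- **Statistical Methods, opening sentences.** "Univariate descriptive statistics and frequency distributions will be calculated for all variables".
- **Safety Assessment.** "The type of AE, severity of AE, and relationship to the study intervention will be recorded". Adverse events are elicited by an open question at the End of Study visit, and Group 2 has an abdominal x-ray to confirm that the capsules have passed.
- **Design Considerations.** "After establishment of safety and efficacy in this population, subsequent studies will be conducted in drug-dependent populations".

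Nowhere do the documents define similar, set a margin, or plan an estimate or confidence interval for the difference in adverse events. The power statement under Sample Size Justification is for Aim 1 only.

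**The concern.** The hypothesis and the test point in opposite directions. A chi-square can give evidence that two rates differ. When it fails to do so, the rates may be close, or the trial may be too small to tell. With 20 per arm the second explanation is always available. Since no estimate or interval accompanies the test, the p-value is the only between-arm result the plan names, and it cannot support the hypothesis it is attached to.

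The unit is a second problem. The sentence compares numbers of events. A Pearson chi-square needs each independent observation to fall in exactly one cell. A participant with three complaints would enter three times, and the event total in an arm could exceed 20, in which case no table with 20 participants per row exists. Two analysts could run different tests from the same sentence.

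What is at stake is the safety statement this trial passes on. Later studies in drug-dependent people are to follow once safety and efficacy are established here, so a report of similar rates resting on a non-significant test would claim more than the data show.

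**Working it through.** **Inputs.** From the documents: 20 participants per arm and a Pearson chi-square. Assumed, because the documents do not give them for Aim 2: two-sided alpha 0.05 (stated only for Aim 1), no continuity correction, the participant with at least one adverse event as the unit, and the event rates shown below.

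**The plan's own figure.** Aim 1 states 80% power with 20 per arm for Cohen's d = 0.95. A two-sample t-test needs 18.4, rounded up to 19 per arm, and 20 per arm gives 83.3% power. The figure is sound and slightly conservative, but it concerns adherent days. There is no corresponding figure for adverse events.

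**1. What identical results would show.** The Newcombe 95% interval combines the Wilson limits of each arm. For 2/20 the Wilson limits are 0.028 and 0.301. For 2/20 against 2/20 the half-width is √[(0.100 − 0.028)² + (0.301 − 0.100)²] = 0.214, so the interval is -21 to +21 points. In the same way, 4/20 against 4/20 gives -25 to +25, and 6/20 against 6/20 gives -27 to +27.

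**2. How large an observed excess stays non-significant.** For 12/20 against 6/20 the pooled rate is 18/40 = 0.45. The standard error is √(0.45 × 0.55 × 2/20) = 0.157, z = 0.30/0.157 = 1.91, and p = 0.057. The difference is 30 points with an interval of -1 to +54. One more ID-Cap participant with an event (13/20) gives p = 0.027. At a lower rate, 7/20 against 2/20 gives p = 0.058, a difference of 25 points and an interval of -1 to +48.

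**3. How often a real excess is missed.** Summing the two binomial distributions over all outcomes where the uncorrected chi-square gives p ≥ 0.05, for a true 20-point excess on ID-Cap:

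| Standard capsule | ID-Cap | Power | Non-significant |
|---|---|---|---|
| 5% | 25% | 0.444 | 56% |
| 10% | 30% | 0.357 | 64% |
| 20% | 40% | 0.291 | 71% |
| 30% | 50% | 0.245 | 75% |

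**4. Whether counting events would help.** Suppose events were independent (Poisson) with equal exposure. Then 6 against 6 events leaves an exact 95% interval for the rate ratio of 0.27 to 3.74. Repeated events within a participant would usually make the true uncertainty larger.

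**5. Whether a formal equivalence test is within reach.** With two one-sided tests at 0.05, 80% power, a true difference of zero and an assumed 20-point margin, n per arm = 2p(1 − p)(1.645 + 1.282)²/0.20². The constant is 8.567/0.04 = 214.2.

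| Event rate p | 2p(1 − p) | n per arm |
|---|---|---|
| 5% | 0.095 | 21 |
| 10% | 0.18 | 39 |
| 20% | 0.32 | 69 |
| 30% | 0.42 | 90 |

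Only the 5% case comes close to 20 per arm. There the expected count is 20 × 0.05 = 1 participant per arm, too few to trust the normal approximation.

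**The case against.** The strongest reply is that the misuse is hypothetical. The aim is labelled exploratory and framed as documentation, and no sentence says that p > 0.05 will be taken as similarity. This stands and is the main reason for the low weight. It does not remove the mismatch, because the plan offers no other rule for judging the hypothesis.

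A reader might infer that the step to drug-dependent populations rests on this chi-square. The documents do not support that. Design Considerations does not tie the step to any one analysis. Safety is also judged from the Group 2 x-ray, from assessment of severity, seriousness, relatedness and expectedness (section 5.7), and from twice-yearly reports that include adverse events (section 5.10). None of these is a between-arm estimate, so they limit the consequence without closing the gap.

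A reader might also infer that type and severity will go unreported by arm, so that symptoms such as "discomfort in the form of pressure sensations in the esophagus upon ingestion" are lost in an all-cause total. That is unproven. Descriptive statistics are promised for all variables, and the detailed monitoring plan mentioned in sections 5 and 5.11 is not among these documents and may specify safety tables.

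Nor does a Pearson chi-square require a yes/no outcome. A table of none, mild, moderate or severe by arm, with one category per participant, would be valid and would suit the aim. The defect is that the plan refers to events and never fixes one category per participant.

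Finally, a margin-based test is not out of reach at every rate: the 5% row above needs about 21 per arm. The case against proposing one depends on event rates the documents do not give.

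**Conclusion.** The point holds, at low severity. The stated test cannot support the stated hypothesis, and a comparison of event counts does not give independent observations. On the assumptions listed, identical results would still leave differences of about 21 to 27 points either way at observed rates of 10% to 30%. A doubling from 6/20 to 12/20 would be non-significant, and a true 20-point excess would be missed in 56% to 75% of trials. The exact figures depend on assumed rates, alpha and an uncorrected test. The conclusion does not, since it holds across the whole range shown. The primary adherence analysis is unaffected. The finding does not extend to saying that the sponsor will declare the arms similar on a p-value, or that the safety judgement rests on this test alone.

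**What to change.** Revise the Exploratory Aim 2 text under Statistical Methods in three ways:

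1. Define the unit as the participant with at least one adverse event, so that each person is counted once.
2. Report the number and percentage per arm, and the risk difference with its 95% confidence interval (for example Newcombe), beside the chi-square.
3. Add a sentence such as: *A non-significant result will not be read as showing similar rates; the confidence interval gives the differences that the data do not rule out.*

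An equivalence test is not proposed, because a 20-point margin would need more than 20 per arm at every rate examined. A by-arm table of type, worst severity and relationship would be useful, but it is optional.

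The cost is a few lines of wording. No new data, visits or participants are needed. The downside is a weaker safety statement: the trial could report the range of differences not excluded, but could not say that rates were similar.

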1. RISKS TO THE SUBJECTS

a. Human Subjects Involvement and Characteristics

Admission into the study is open to men, women, and children 18 to 65 years of age, and to all racial and ethnic groups. We anticipate we will screen (by telephone or in person) about 60 potential subjects. A total of 40 healthy men and women will be enrolled. We will recruit subjects from multiple

Program Director/Principal Investigator (Last, First, Middle): [name]

sources, primarily through advertising in local media via television, newspaper, and word of mouth among subjects.

Inclusion Criteria

- Must be between the ages of 18 and 65 years.
- If female and of childbearing potential, must agree to use acceptable methods of birth control for the duration of the trial.
- Must consent to random assignment, and be willing to commit to capsule ingestion.
- Must be able to read and provide informed consent.
- Must function at an intellectual level sufficient to allow accurate completion of assessments.
- Must have a Body Mass Index (BMI) below 35.

Exclusion Criteria

- Women who are pregnant, nursing, or plan to become pregnant during the course of the study.
- Must not have evidence of a significant medical condition which may affect capsule passage through the gastrointestinal tract (including, but not limited to, Crohn's disease, small bowel tumors, intestinal adhesions, ulcerations, and radiation enteritis) Must not have a current major psychiatric disorder as these may interfere with assessment measures.
- Must not meet DSM-V criteria for moderate to severe substance dependence (other than nicotine or caffeine) within the past 60 days
- Hypersensitivity to riboflavin or any other capsule component.
- Individuals with embedded electronic devices.
- Patients who, in the investigator's opinion, would be unable to comply with study procedures or assessments, or would be unacceptable study candidates (e.g., poses threat to staff).

b. Sources of Materials

- 1) Research material obtained from individual subjects includes questionnaires and interviews with study personnel as well as urine samples. To ensure confidentiality, all subject data will be number coded, and only the investigators will have access to the master lists of codes.
- 2) The research material will be obtained specifically for research purposes. Written research material obtained will be stored in the Addiction Sciences Division, in an office that is locked when not in use. Any quantitative riboflavin urine samples collected during the study will be stored in the MUSC Clinical Neurobiology Laboratory..

c. Potential Risks

Potential risks associated with capsule ingestion include discomfort in the form of pressure sensations in the esophagus upon ingestion (typically lasting less than 30 seconds), risk of endoscopy pill retention, and a rare risk of capsule aspiration upon attempting to swallow the capsule. There is the risk of breach of confidentiality.

2. ADEQUACY OF PROTECTION AGAINST RISKS

a. Recruitment and Informed Consent

Patients will primarily be recruited through the use of advertisements (internet, newspaper). Respondent-driven sampling will also be utilized. Medical records will NOT be reviewed to identify potential study subjects. The study PI, a Co-I, or other qualified study staff will obtain informed consent. The informed consent form includes a detailed description of the study procedures, along

Program Director/Principal Investigator (Last, First, Middle): [name]

with statements regarding participants' rights to withdraw from the procedure at any time without consequences. The informed consent form will be explained to subjects in easy-to-understand language, and subjects will be instructed to read the form carefully prior to signing it. Consent will be documented by the signature of the participant on the informed consent agreement, accompanied by the signature of the individual obtaining the consent.

b. Protection Against Risk

[name] and the study physician assistant will monitor for medical and psychiatric stability. All study visits will be conducted under the supervision of experienced personnel. If crisis intervention is necessary, senior staff will be available to evaluate the subject and provide an intervention or referral. If hospitalization is indicated, the patient will be hospitalized through the CDAP program at MUSC or an appropriate referral will be made. All subjects will be fully informed that they may withdraw from the study at any time without penalty. All subject records will be kept in a locked filing cabinet, and confidentiality of all materials will be maintained. Offices also will be locked at times when not in use.

Subjects will be taught about potential side effects of ID-Cap ingestion and will be closely followed by psychiatrists, a PharmD, and other members of the research team. Subjects will be excluded from participation if a medical condition is present that may impact capsule passage, and subjects will also be excluded if they have a known hypersensitivity to any capsule component. Adverse events will be assessed at the End of Study visit, and all subjects will be provided with an after-hours emergency contact number in the event that an adverse event occurs when the clinic is closed.

To ensure confidentiality, subject data will be number coded, and only the investigators will have access to the master lists of codes. All patient records will be kept in an office that will be locked at times when not in use. The research staff understands the importance of maintaining confidentiality. This method of maintaining confidentiality has been used for several years by our research group and has been effective.

Data from the loaner smartphones will be immediately transmitted to RedCap, a secure data management system maintained at MUSC (See Section 5.3, Data Management and Analysis). These data will only be accessible by the Research Personnel and PI. Participants will be informed of these potential risks during the informed consent process and will have the option to leave the study at any point.

The smartphone application is equipped to transmit data directly into RedCap with de-identified subject IDs. Server maintenance will be conducted by Information Technology Specialists at MUSC. Once data have been transmitted to RedCap from the loaner smartphone or participant's personal smartphone, no personal information will be stored on the device. Any information that is stored on the phones will be de-identified. If the loaner iPhone is lost or stolen, devices will be reset immediately.

